As has been outlined in the Preliminary Results section of this proposal, *anti*-[¹⁸F]FACBC has been demonstrated to 1) have high sensitivity in the detection of recurrent prostate carcinoma though with suboptimal specificity in the prostate bed, and 2) the ability to differentiate prostatic from extraprostatic recurrence with high accuracy. *anti*-[¹⁸F]FACBC may thus have specific advantages for imaging recurrent prostate neoplasia within a clinical setting over conventional imaging. Yet, MR, especially with the addition of diffusion weighted imaging, has been reported in preliminary studies to provide high accuracy especially in the characterization of prostate bed recurrence. We hypothesize that utilization of a transmolecular approach combining synthetic amino acid radiotracer PET imaging with multiparametric MR has the potential to identify the presence and location of recurrent prostate carcinoma to a higher accuracy than either modality alone. **Therefore the most comprehensive manner to assess our hypothesis that PET-CT imaging with *anti*-[¹⁸F]FACBC in combination with multiparametric MR will lead to improved patient care resulting from detection of local and distant recurrent disease (Specific Aim #1) is to undertake a prospective clinical trial designed to address these issues.**

Secondary Aims

Aim 2. To determine mRNA differences between prostate carcinoma recurrent in the prostate bed and extraprostatic locations and to correlate any difference with quantifiable imaging biomarker data such as SUV for *anti*-[¹⁸F]FACBC PET-CT and ADC for MR.

Within the structure of the clinical trial (the same 25 patients) we will obtain sufficient tissue to perform mRNA sequencing on samples to exploit differences between the genetic profiles of recurrent prostate carcinoma in the prostate bed versus metastases. Since approximately 30% of patients with PSA > 4 ng/ml by our experience manifest with both prostate bed and nodal recurrence, we believe at least 8-10 patients in whom this comparison can be directly made will be available for analysis. This may also occur with lower PSA levels with faster DT. We will then correlate any differences in genotypic profile with imaging biomarkers from synthetic amino acid PET and MR, such as SUV and ADC.

Sub-aim 2a. To evaluate protein expression of previously identified amino acid transporters (AATs) that have been implicated in the uptake of *anti*-[¹⁸F]FACBC.

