Also within the context of the clinical trial of 25 patients, we will, whenever there is sufficient tissue, determine if candidate amino acid transport (AAT) proteins identified from data obtained in an earlier study (Project 1: P-50 ICMIC) are expressed. We will perform IHC analysis of up to 7 candidate AAT or co-transporters, specifically PAT 1, LAT1, LAT2, 4F2hc, and ASCT2, LAT3 and ASCT1 to understand if the AAT whose mRNAs are increased in malignant prostate carcinoma and correlated with *anti*-[¹⁸F]FACBC uptake are expressed at the protein level by IHC analysis.

Rationale for Aim 2 and Sub-aim 2a.

As has been outlined in the Preliminary Results section of this proposal, there is preliminary data in the literature of gene expression and mutational differences between primary prostate carcinoma cells and those prostate metastases [7-9] as well as between bone metastases and non-osseous metastases [8]. We propose within the context of this clinical trial to provide tissue to further understand these differences both in the ability of prostate carcinoma to transport and retain amino acids measured as uptake of *anti*-[¹⁸F]FACBC and expression characteristic as studied by multiparametric MR such as ADC parameters on DWMR and uptake and retention of Gadolinium. If we can determine that there are gene expression differences between malignancy confined to the prostate bed and those that are extraprostatic, we can correlate these differences to PET uptake and MR appearance. Furthermore, we may also be able to derive incidental genotypic information that could be exploited on subsequent unrelated experiments. In addition, we have preliminary evidence based on our earlier research that PAT1, LAT2 and ASCT2 as well as LAT1, xCT, LAT3 and ASCT1 were associated with malignancy. Out of the AATs that were associated with malignancy, PAT1 expression had the strongest correlation coefficient relative to *anti*-3-[¹⁸F]FACBC uptake [38]. We believe that a study such as this one provides an ideal opportunity to obtain both prostatic and extraprostatic tissue from the same patient in order to test these hypotheses using the patient as his own control.

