Our rationale for utilizing patients with PSA ≥ 4 is as follows. A total of 127 patients have been studied already in an R-01 study of the diagnostic performance of *anti*-3-[¹⁸F]FACBC versus conventional imaging. If the patients are stratified by PSA level as in the table below, 41/73 were positive in the prostate bed only, 25 in both prostate bed and lymph nodes, and 1 in lymph nodes only. Thus, in the 25 patients whom will be studied in this population,

approximately 23 will be expected to have disease in the prostate bed and approximately 9 will have disease in nodes, most of the latter will also have disease in the prostate bed. This should provide sufficient tissue for the above secondary aims. In addition, we have demonstrated that greater extraprostatic involvement will occur with shorter DT even at lower PSA levels. Thus the addition of PSA 2.0-3.99 ng/ml plus DT \leq 10 months is a reasonable method to increase recruitment while still acquiring tissue from extraprostatic involvement.

PSA group	<4 (n=54)	\geq 4 (n=73)	Total(n=127)
Prostate bed only (+)	27	41	68
LN only (+)	3	1	4
Both	8	25	33
Total	38	67	105

We hypothesize that by identification of disease recurrence in the prostate bed and extra-prostatic locations, we can exploit differences in mRNA analysis to correlate these differences to synthetic amino acid transport as well as MR parameters such as ADC mapping, and also better understand the relationship of AAT protein expression to *anti*-3- ^{18}F FACBC uptake. **Therefore the most comprehensive manner to obtain tissue to test our hypotheses is within the context of this prospective clinical trial.**

[figure not shown]
C1.0 Research Design and Methods (Aim 1)

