Upon completion of the study and/or after additional follow-up, each patient may be re-reviewed by the same Ground Truth Panel to determine if the predicted findings on *anti*-[¹⁸F]FACBC scan and MR individually and in tandem match those of clinical and pathologic findings especially in regard to the identification of prostatic versus extraprostatic recurrence. Also at that time uptake parameters will be reviewed. At no time this study will interfere with proper therapy as determined by the patient's physicians and the patient.

C2.0 Study Design and Methods (Aim2 and Sub Aim 2a)

Rationale. We hypothesize that *anti*-[¹⁸F]FACBC uptake is mediated by a LAT protein subtype or subtypes. However, the precise LAT subtype involved in all cases is unknown. We also further hypothesize that there are genotypic differences between recurrent prostate carcinoma cells confined to the prostate bed and those that are extraprostatic and that these differences can be explored via proper identification of candidate tissue via transmolecular imaging to be performed at termination of study or when sufficient tissue has been collected.

Experimental Design. To test the above hypothesis, we will compare mRNA expression of recurrent prostate carcinoma tissue within the prostate bed and extraprostatic. In addition we will utilize *anti*-[¹⁸F]FACBC avid tissue to confirm that the following AAT subtypes based on preliminary data are expressed at the protein level: PAT 1, LAT1, LAT2, 4F2hc, and ASCT2, LAT3 and ASCT1. We will study 8-10 samples of each recurrent prostate carcinoma in the prostate bed and 8-10 samples of disease outside the prostate bed, preferably in the same patient. We predict that one or more AAT subtypes will be relatively overexpressed by IHC in FACBC-avid carcinoma. We also predict that there will be differences in mRNA expression

based on these tissue samples between disease confined to the prostate bed and those that are extraprostatic. Based upon tissue availability we will perform IHC in the following rank priority: First: PAT 1; Second: LAT1, LAT2, 4F2hc; Third: ASCT2, LAT3 and ASCT1. This priority ranking is based on our desire to first confirm phenotypic expression of PAT1, since presence of this AAT correlated most strongly with *anti*-[¹⁸F]FACBC uptake, followed by LAT1 and LAT2 with the heterodimeric associated protein 4F2hc, and ASCT2, LAT3 and ASCT1.

C 2.1 Quantitative next-generation mRNA sequencing

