Methods. For experiments on fixed tissue RNA will be extracted at the Cancer Genomics Shared Resource (CGSR) at the Winship Cancer Institute from macrodissected 5 micron sections. The CGSR has extensive experience in preparing Total RNA from FFPE tissues [42]. FFPE RNA extraction will be performed using the Omega Biotech methodology in 96-well format on a Kingfisher FLEX Liquid Handler Robot. FFPE RNA will be quantitated by nanodrop spectrophotometry, and tested for RNA integrity and quality by Taqman analysis of the RPL13a ribosomal protein. Samples with sufficient yield (>500 ng), A_{260}/A_{280} ratio > 1.8 and RPL13a C_T values less than 31 cycles will be used for preparing sequencing libraries using the TrueScript kit (Illumina). Amplified cDNA libraries will be sonicated to an average length of 250 bp with a Covaris E-120 Adaptive Focused Acoustics Instrument. We will repair the ends of the sonicated DNA using the Illumina TrueScript protocol and generate barcoded libraries for RNA-seq analysis on an Illumina HiSeq 2000 instrument at the Southern California Genotyping Consortium at UCLA. Agilent Bioanalyzer Nanochip analysis will be performed to ensure the integrity of libraries prior to sequencing. We will obtain 60 million reads per sample of 50bp paired-end sequencing reads using the Illumina version 3 kits with three samples multiplexed per sequencing lane.

Fluorogenic quantitative RT-PCR assays will be used to confirm changes identified by RNA-seq analysis and performed in triplicate with standard SYBR-Green methodology on the I-cycler system (Bio-Rad, Hercules, CA, USA) according to published protocols with minor modifications [43]. Reaction specificity will be assessed by melting point analyses, in which single melting point peaks are required at temperatures predicted by amplicon sequence. Reactions without reverse transcription and template will serve as controls for DNA contamination and specimen carry-over. Test gene expression will be normalized to 28S ribosomal RNA and referenced to a standard RNA specimen. Relative normalized gene expression of each LAT subtype will be compared in FACBC avid versus non-avid prostate carcinoma, with statistical significance assessed by analysis of variance (ANOVA).

C 2.2 Immunohistochemistry

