Depending on the normality of data distribution, t-test or Wilcoxon rank sum test will be conducted to compare the mRNA differences, genomic differences in gene expression, alternative splicing, indels and single base mutations between prostate carcinoma recurrent in the prostate bed and extraprostatic samples. Analysis of variance (ANOVA) will be used to compare the IHC staining of protein levels between the different categories of FACBC uptake. Tukey pairwise comparison will be further conducted when the overall comparison with ANOVA

Version 9-23-13

Version 11-6-13

Version 11-11-14

Version 12-4-14

is significant at the significance level of 0.05. Pearson/Spearman correlation coefficients will be estimated to measure the associations: 1) between mRNA levels of candidate AAT genes and FACBC uptake; 2) between mRNA differences and quantifiable imaging biomarker data such as SUV for *anti*-[¹⁸F]FACBC PET-CT and ADC for MR. Multivariate analyses will further be conducted, in which general linear model (GLM) will be employed to assess the adjusted relationships mentioned above after adjusting for the other covariates.

Sample size and power calculation

The sample size of this study is 25 patients. The power calculation is based on the comparison of mRNA differences between the prostate bed and extraprostatic samples using two sided t-test. At the significance level of 0.05, the sample size of 25 will achieve a power of at least 80% to detect one standard deviation or higher difference in mRNA difference between the two groups of samples.

F. Adverse Event Reporting

An adverse event is defined as any untoward medical occurrence associated with the use of a drug in humans whether or not considered drug-related

A significant shift from baseline which can be attributable to the radiotracer injection and not the patient's medical condition will be considered an unexpected AE. An event greater than 7 days post scan will not be considered an AE since 95% of ligand is eliminated by 7days.

The National Cancer Institute's Common Terminology Criteria for Adverse Events (CTCAE) Version 4.03 (June 14, 2010) will be used as a guide address potential AEs subject to limitations above and medical and scientific judgment as to plausibility of such criteria in a diagnostic radiotracer study.

Adverse Event Reporting

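### The only power statement takes the 25 enrolled patients as its n; at the 8-10 samples per site the plan expects, power at 1 SD is about 46-56% unpaired or 68-80% paired.

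*Combined protocol and SAP*

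**What the plan says.** The paragraph on sample size and power at the end of section E2.0 gives the study size as 25 patients. It bases power on a two-sided t-test of mRNA between prostate-bed and extraprostatic samples at the 0.05 level, and concludes that "the sample size of 25 will achieve a power of at least 80% to detect one standard deviation or higher difference in mRNA difference". It does not say whether the test is paired or which standard deviation is meant. The planned analysis in the same section is that a "t-test or Wilcoxon rank sum test will be conducted to compare the mRNA differences".

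Elsewhere the plan gives the amount of tissue it expects:

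- Secondary Aims, Aim 2: "Since approximately 30% of patients with PSA > 4 ng/ml by our experience manifest with both prostate bed and nodal recurrence", and therefore "we believe at least 8-10 patients in whom this comparison can be directly made will be available for analysis".
- Rationale for Aim 2 and Sub-aim 2a, next to the PSA table: of the 25 patients, "approximately 23 will be expected to have disease in the prostate bed and approximately 9 will have disease in nodes".
- C2.0: "We will study 8-10 samples of each recurrent prostate carcinoma in the prostate bed and 8-10 samples of disease outside the prostate bed", with same-patient samples preferred but not required.
- Rationale for Aim 2 and Sub-aim 2a: the study is presented as a chance to "obtain both prostatic and extraprostatic tissue from the same patient in order to test these hypotheses using the patient as his own control".
- C 2.1: extracted RNA must also pass yield, purity and quality limits; among these, only samples with RPL13a C_T "values less than 31 cycles will be used for preparing sequencing libraries".

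**The concern.** A comparison of tissue from two sites is limited by the scarcer site. Every enrolled man may be a candidate for bed tissue, but only those with disease outside the bed can give an extraprostatic sample, and the plan puts that at about 9. The power sentence nevertheless attaches at least 80% power to 25.

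This is the only power statement in the document; Aim 1 has no power or precision figure. If it is wrong for the tissue that will exist, a reader cannot tell what the mRNA comparison can detect, and a null result could be taken as evidence of no difference when the test had little chance of finding one. The missing details add to this. The rank sum alternative and the reference to two groups of samples suggest independent groups, while the patient-as-own-control rationale suggests pairs. The two give different power at the same number of samples.

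**Working it through.** **Inputs.** Two-sided 0.05, a true difference of 1 SD and a target of at least 80% (E2.0); 25 enrolled (E2.0); 8-10 samples per site (C2.0); about 23 men with bed disease and about 9 with nodal disease (Rationale for Aim 2). All figures are for one gene.

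**Formulas.** Exact power from the noncentral t distribution, with difference d in SD units:

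- Unpaired: noncentrality d / sqrt(1/n1 + 1/n2), with n1 + n2 - 2 degrees of freedom.
- Paired: noncentrality d × sqrt(n), with n - 1 degrees of freedom, where d is in SDs of the within-patient difference.

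Power is the probability that |t| exceeds the two-sided 5% critical value.

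**Step 1. The plan's own figure.** With n = 25 and d = 1:

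| Reading of 25 | Power |
|---|---|
| 25 samples per site, unpaired | 93.4% |
| 25 pairs, SD of differences | 99.8% |
| 25 samples in total, split 13/12, unpaired | 66.7% |

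The stated lower bound is true for 25 per site or 25 pairs and false for 25 samples in total. For an unpaired test the bound is first met at 17 per site (80.7%; 16 per site gives 78.1%).

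**Step 2. The tissue the plan expects, unpaired.** For example, at 8 per site the noncentrality is 1 / sqrt(1/8 + 1/8) = 2.00, against a critical value of 2.145 on 14 degrees of freedom.

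| Samples per site | Power at 1 SD | Difference detectable at 80% power |
|---|---|---|
| 8 and 8 | 46% | 1.51 SD |
| 9 and 9 | 51% | 1.41 SD |
| 10 and 10 | 56% | 1.33 SD |
| 23 and 9 (all expected disease) | 69% | 1.14 SD |

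The last row is a favourable bound. C2.0 does not plan it, and most node-positive men are also expected to have bed disease, so the two groups would not be independent.

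**Step 3. The same tissue, paired, with 1 SD of the within-patient difference.** At 10 pairs the noncentrality is sqrt(10) = 3.16, against a critical value of 2.262 on 9 degrees of freedom.

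| Pairs | Power at 1 SD | Difference detectable at 80% power |
|---|---|---|
| 8 | 68% | 1.16 SD |
| 9 | 75% | 1.07 SD |
| 10 | 80.3% | 1.00 SD |

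**Step 4. Paired, but with 1 SD of single samples.** The effect becomes 1 / sqrt(2(1 - rho)), where rho is the within-patient correlation. The documents give no value for it, so the range is an assumption. For rho from 0 to 0.7, power is 41-88% with 8 pairs, 46-92% with 9 and 51-95% with 10. Reaching 80% needs rho of about 0.63, 0.56 and 0.50 respectively.

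**Step 5. How likely 10 pairs are.** The 30% rate in Aim 2 gives 0.30 × 25 = 7.5 men with both sites. The PSA table gives 25/73 × 25 = 8.6. If each of the 25 men independently has both sites with one of these probabilities, the chance of 10 or more such men is 19% or 34%. These rates come from men with PSA of about 4 ng/ml or more. The plan gives no rate for the men it also admits at 2.0-3.99 ng/ml with a short doubling time, so this step is indicative only. Samples lost to insufficient tissue or to the RNA quality limits would reduce the count further.

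**The case against.** The best defence is that 25 was never meant as the number per group. Read generously, the sentence says that enrolling 25 men yields enough tissue, and 10 pairs at 1 SD of the within-patient difference do give 80.3%. The own-control rationale and the preference for same-patient tissue fit that reading, the expected tissue yield is openly stated, and on the single-sample SD scale a high enough within-patient correlation would lift power above 80%. The plan also calls the trial preliminary, and it has a tissue-yield argument beside the PSA table, so the power sentence is not the only thing said in support of 25.

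Part of this stands. The figure is not a slip of calculation, since the bound is sound for 25 per site. The shortfall is not certain under every paired reading. The tissue-yield paragraph is some support, although it takes 25 as given and argues for the PSA threshold.

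The 10-pair reading, however, is not in the text. The sentence names 25, refers to two groups of samples, and sits beside a rank sum test, which is an unpaired test. Ten pairs is the top of the expected range, and the plan's own rates point to 7.5 to 8.6 men. Disclosing 8-10 samples elsewhere does not repair a power statement that does not use that number.

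**Conclusion.** The concern holds. The stated power of at least 80% at 1 SD belongs to an amount of tissue that the plan does not expect to have. At 8-10 samples per site, an unpaired test would miss a true 1 SD difference in one gene 44-54% of the time. A paired test would miss 1 SD of the within-patient difference 20-32% of the time. The sentence implies 20% or less.

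The unpaired shortfall rests only on the plan's own numbers and persists even with all expected disease sampled (69%). The paired result depends on which SD is meant and, on the single-sample scale, on a correlation that the documents do not supply. All figures are for a single gene at 0.05; any multiplicity correction across genes would lower them. The aim is secondary and the Aim 1 accuracy estimates are unaffected, but the statement is wrong for the expected tissue and should be corrected.

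**What to change.** Replace the power sentence in E2.0 with figures for the expected tissue, and name the test and the SD. Suggested text:

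> Twenty-five patients will be enrolled; this is not the number analysed for Aim 2, for which 8-10 samples per site are expected. For a single gene at two-sided 0.05, an unpaired t-test with 8-10 samples per site has 80% power to detect a difference of 1.33-1.51 SD (46-56% power at 1 SD).

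If same-patient tissue is to be analysed as pairs, name the paired t-test, with the signed-rank test as the nonparametric alternative, and replace the last sentence with:

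> For a single gene at two-sided 0.05, 8-10 pairs give 80% power to detect 1.0-1.16 SD of the within-patient difference (68-80% power at 1 SD).

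The cost is a wording change and a less favourable power figure. Naming a paired test would also be a small change to the planned analysis. No extra patients or procedures are needed. The new text still describes a single-gene t-test and does not give the power of the transcriptome-wide analysis in C 2.3, so it should not be presented as doing so.
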